CLINICAL INVESTIGATIONAL PROTOCOL

TITLE:

Single-Laser PVI: Single-encirclement Laserballoon ablation for Pulmonary Veins Isolation

STUDY N°:

STUDY NAME: Single-Laser PVI

VERSION: 2.0, 27/08/2019

I, the Investigator, have examined this Clinical Investigational Protocol for the Clinical Trial entitled: *Single-Laser PVI: Single-encirclement Laserballoon ablation for Pulmonary Veins Isolation*
I agree to conduct the Clinical Trial according to this Clinical Trial Protocol and to comply with its requirements, subject to ethical and safety considerations.

INVESTIGATOR

NAME: [name]

DATE: 28-08-2019

SIGNATURE: 

« Any and all information presented in this document shall be treated as confidential and shall remain the exclusive property of the Sponsor. The use of such confidential information must be restricted to the recipient for the agreed purpose and must not be disclosed, published or otherwise communicated to any unauthorized persons, for any reasons, in any form whatsoever without the prior written consent of the Sponsor »

PRINCIPAL INVESTIGATOR

Name: [name]
Aritmologia I.R.C.C.S. Policlinico San Donato
[contact]
E-mail: [contact]

SPONSOR

I.R.C.C.S. Policlinico San Donato
[name]

[figure not shown]
PROTOCOL SYNOPSIS

Title:	Single-Laser PVI: Single-encirclement Laser balloon ablation for Pulmonary Veins Isolation
Acronym:	Single-Laser PVI
Aim:	To assess the efficacy of laser balloon ablation of atrial fibrillation (AF) without verification of electrical isolation of pulmonary veins using implantable loop recorder.
Objectives:	
Primary:
 
 • Acute and 1-year outcome of the ablation procedure. 
Secondary:
 
 • Assessment of safety and procedural times of the ablation procedure.
Endpoints:	
Primary:
 
Success rate at 1-year, defined as:
 
 • Free from AF, atrial tachycardia and flutter documented with ILR/Holter monitoring without antiarrhythmic drugs. 
Secondary:
 
 - Procedural and 1-year complications related to the ablation procedure. - Absence of AF inducibility with programmed extrastimulation at the end of the procedure, before and after isoproterenol administration. - Procedural time of the ablation procedure. - Fluoroscopy time of the ablation procedure. - Time to first symptomatic AF recurrence. - Time to first asymptomatic AF recurrence. - Need for a redo ablation procedure. - Need for antiarrhythmic drugs. - AF Burden quantified with ILR/Holter monitoring at follow-up visits.
Study design and duration:	
Prospective, open, single-center study
 
The patients indicated to AF ablation procedure will be treated with laser balloon ablation and, as per normal clinical practice; the procedure efficacy will be monitored with an ILR, which will be implanted one month (\pm 15 days) after the ablation procedure, or with evaluation of a cardiac holter monitoring at 3, 6 and 12 months after ablation. The enrolled patients will be followed with 3-month, 6-month and 1-year visits.
 
The overall duration of the study is expected to be 24 months with ~ 12 months of enrolment phase.

Used device:	
 - HeartLight Endoscopic Ablation System (CardioFocus, Inc, Marlborough, MA)

Study population	Patients with paroxysmal or persistent AF who have indications for the first time ablation procedure according to the ESC / EHRA recommendations (European Society of Cardiology / European Heart Rhythm Association).
Inclusion/Exclusion criteria	
Inclusion criteria
 
 1. Age between 18 and 85 years 2. Paroxysmal or persistent AF 3. Patients AF who have indications for the first time ablation procedure according to the ESC / EHRA recommendations (European Society of Cardiology / European Heart Rhythm Association). 4. Ability to provide written informed consent for study participation and be willing and able to comply with the study evaluations and follow up schedule 
Exclusion criteria
 
 1. Previous AF ablation procedures 2. Secondary AF due to other causes 3. Hyperthyroidism 4. Left ventricular ejection fraction <30% 5. NYHA class IV 6. Left atrium area > 35 cm² 7. Severe disease of cardiac valves 8. Contraindication to anticoagulant therapy 9. Presence of thrombus in the left atrium 10. Myocardial infarction or unstable angina or recent coronary artery bypass (<6 months) 11. Thoracic surgery for congenital, valvular or aortic disease 12. History of cerebrovascular events 13. Pregnancy 14. Significant comorbidity, such as cancer, severe kidney failure requiring dialysis, severe obstructive pulmonary disease, cirrhosis, with a life expectancy of less than 2 years 15. Contraindications are present as indicated in the “instructions for use” of the devices used
Statistical considerations	
In a recent meta-analysis including 1188 patients, free from arrhythmic recurrences at 12 months after a single ablative procedure with a laser balloon and without continuous monitoring with ILR was 74%¹.
 
Assuming that the approach without post-ablative verification of pulmonary vein isolation and continuous monitoring with ILR/Holter ECG can lead to a 60% success rate at 12 months, 80 patients are required to have an 80% probability to observe a level of 2-code significance of 0.05 in an exponential model with the log rank test. With an estimated loss of data (patients lost to follow-up, protocol deviations and incomplete data) of 5%, the total number of patients to be enrolled is 82.
 
Descriptive statistics (arithmetic mean, median as indicated, minimum and maximum and standard deviation) will be calculated for quantitative variables. Absolute frequencies and percentages will be obtained for qualitative variables. Summary statistics and 95% confidence intervals

Data collection	
will be presented. Unpaired the Student's t test will be used to compare continuous variables and with the chi-square test for categorical variables, as appropriate. All tests are two-tailed.
 
A detailed statistical analysis plan will be finalized before performing the analysis.
 
- Before ablation procedure: collection of standard data for patients undergoing AF ablation.- During ablation procedure: procedural and fluoroscopy times.- After ablation procedure: arrhythmic recurrences at 3-month, 6-month and 1-year follow-up.
-----------------	--

1. STUDY FLOW CHART

	Screening Enrolment	Procedure	Discharge	3M FUP	6M FUP	1Y- FUP
Inclusion/Exclusion criteria	X					
Informed consent	X					
Medical history, demographic data, drug therapy	X°					
12-lead ECG	X°	X°	X°	X°	X°	X°
Echocardiography	X°			X°	X°	X°
Holter ECG				X°	X°	X°
Pregnancy test	X°					
AF burden				X°	X°	X°
Symptoms	X°	X°	X°	X°	X°	X°
Ablation procedure times		X				
AF/AT recurrences				X°	X°	X°
Adverse events		X°	X°	X°	X°	X°
Antiarrhythmic drugs	X°	X°	X°	X°	X°	X°

M= Month

Y= Year

° as clinically indicated

3. LIST OF ABBREVIATIONS

RFCA: radiofrequency catheter ablation;
AF: atrial fibrillation
PVI: pulmonary veins isolation
ILR: implantable loop recorder
PI: principal investigator
CRF: case report form
AE: adverse event
SAE: serious adverse event
SADE: Serious Adverse Device Effect
EC: ethics committee

4. INTRODUCTION AND RATIONALE

In the last three decades, radiofrequency catheter ablation (RFCA) has developed from an experimental procedure to a valid and well established treatment option for many patients affected by atrial fibrillation (AF)².

Despite improvements in this technology, arrhythmic recurrences are still present and often are linked to electrical gaps in pulmonary veins isolation (PVI). These and other factors have led to research of new technologies. Recently, a new promising technology has been developed for PVI: the laser balloon ablation. The HeartLight Endoscopic Ablation System (CardioFocus, Inc, Marlborough, MA) is designed to achieve PVI with a catheter that includes several unique features including a compliant balloon and a small endoscope, used to aim an adjustable arc of laser energy. Worldwide experiences with laser balloon are growing and a recent meta-analysis on 1188 patients has showed an estimate of 12-month freedom from recurrences of 74%¹. These data were obtained performing the verification the veins isolation with a mapping catheter positioned within the target PV ostium at the end of the procedure. This additional step may length the procedural and fluoroscopy times, increasing also the risk of complications without proven benefits. In our clinical practice, this additional check of PVI is not performed. In addition, all the available data on the success rate of laser balloon ablation were provided without continuous heart rate monitoring. It is well known that AF recurrences are often asymptomatic and studies on AF ablation efficacy should apply a continuous monitoring approach.

In this observational study, we aim to assess the efficacy at 1-year of AF laser balloon ablation without verification of electrical PVI using implantable loop recorder (ILR) monitoring.

5. STUDY OBJECTIVES

5.1 Primary

The purpose of this prospective clinical study is to assess in a patients with paroxysmal or persistent AF the 1-year clinical outcome of the laser balloon ablation without verification of electrical PVI using ILR monitoring.

5.2 Secondary

The Assessment of safety and procedural times of the laser balloon ablation procedure.

6. ENDPOINTS

6.1 Primary Endpoint

Success rate at 1-year, defined as:

Free from AF, atrial tachycardia and flutter documented with ILR or Holter ECG monitor without antiarrhythmic drugs.

6.2 Secondary Endpoint

- Procedural and 1-year complications related to the ablation procedure.
- Procedural time of the ablation procedure.
- Fluoroscopy time of the ablation procedure.
- Time to first symptomatic AF recurrence.
- Time to first asymptomatic AF recurrence.
- Need for a redo ablation procedure.

- Need for antiarrhythmic drugs.
- AF Burden quantified with ILR/Holter ECG at follow-up visits.

7. STUDY DESIGN

7.1 Description of the Protocol

This is a prospective and single-center study. A targeted number of 82 patients suffering from paroxysmal or persistent AF, indicated to undergo catheter ablation will be included. The study will consist of: i) patient enrolment, ii) treatment phase, and iii) 1-year follow-up phase. The duration of the study is expected to be 24 months, from first patient enrolment to last patient follow up.

7.2 Number of subjects required to be included in the study

In a recent meta-analysis including 1188 patients, free from arrhythmic recurrences at 12 months after a single ablative procedure with a laser balloon and without continuous monitoring with ILR was 74%¹.

Assuming that the approach without post-ablative verification of pulmonary vein isolation and continuous monitoring with ILR can lead to a 60% success rate at 12 months, 80 patients are required to have an 80% probability to observe a level of 2-code significance of 0.05 in an exponential model with the log rank test. With an estimated loss of data (patients lost to follow-up, protocol deviations and incomplete data) of 5%, the total number of patients to be enrolled is 82.

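### The enrolment target of 82 does not allow for the stated 5% loss: 80 evaluable patients need 85 enrolled, and 82 leaves about 78

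*Protocol*

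**What the plan says.** Section 7.2 of the protocol builds the sample size in two steps. The first gives the number needed for analysis: "80 patients are required to have an 80% probability to observe a level of 2-code significance of 0.05 in an exponential model", using a log-rank test. The reference rate is 74% freedom from recurrence at 12 months, and the rate assumed for this study is 60%. The second step allows for lost data and gives the enrolment figure: "patients lost to follow-up, protocol deviations and incomplete data) of 5%, the total number of patients to be enrolled is 82".

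The synopsis (statistical considerations) and section 13 repeat 80, 5% and 82. Section 7.1 carries only the result: "A targeted number of 82 patients suffering from paroxysmal or persistent AF". Nowhere does the protocol give another loss rate, or a rule other than the 5% allowance, that would lead from 80 to 82.

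**The concern.** The step from 80 to 82 is a single calculation on two stated numbers, and it does not come out. Adding two patients to 80 is an increase of 2.5%, half of the loss the protocol says it expects.

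The 80% power is claimed at 80 patients. If recruitment stops at 82 and the loss is as forecast, the analysis has fewer than 80, so the plan misses its own requirement when everything goes as planned. The same figure stands in the synopsis, 7.1, 7.2 and 13, so it is not an isolated typing slip that another section puts right.

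**Working it through.** **Inputs, all from section 7.2 and repeated in the synopsis and section 13**

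- Patients required: n = 80
- Expected loss of data: d = 5%, covering loss to follow-up, protocol deviations and incomplete data together
- Patients to be enrolled: N = 82

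**Step 1. Try to reproduce 82**

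| Rule | Calculation | Result |
|---|---|---|
| Correct inflation, n / (1 − d) | 80 / 0.95 = 84.2 | 85 |
| Common shortcut, n × (1 + d) | 80 × 1.05 = 84.0 | 84 |
| Protocol | not shown | 82 |

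Neither rule returns 82. Check on 85: 85 × 0.95 = 80.75, which keeps at least 80. Check on 84: 84 × 0.95 = 79.8, just short.

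**Step 2. What 82 delivers**

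- Evaluable patients at 5% loss: 82 × 0.95 = 77.9, about 78
- Largest loss that still leaves 80: 1 − 80/82 = 2.4%

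**Step 3. Which inputs would give 82**

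- A base of 78 with the shortcut: 78 × 1.05 = 81.9
- A loss of 2.5% on 80: 80 × 1.025 = 82.0, or 80 / 0.975 = 82.05

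The protocol states neither a base of 78 nor a loss of 2.5%.

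**Step 4. Effect on power**

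The protocol does not say what the log-rank test compares. To gauge the effect I assume one cohort tested against a fixed reference of 74% at 12 months, a true rate of 60%, exponential times to recurrence, 12 months of follow-up and two-sided 0.05. The hazards per year are −ln 0.74 = 0.301 and −ln 0.60 = 0.511, a ratio of 1.70.

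- *One-sample log-rank.* The statistic is (O − E)/√E, with O the observed recurrences and E the number expected at the reference hazard. Power was simulated with 400,000 runs per row.
- *One-sample proportion.* Power = Φ[(0.14 − 1.96 √(0.74 × 0.26/n)) / √(0.60 × 0.40/n)].

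| Evaluable n | One-sample log-rank | One-sample proportion |
|---|---|---|
| 78 | 79.9% | 77.9% |
| 80 | 80.9% | 78.8% |

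The loss is about one percentage point by either method. The approximate 95% confidence interval around a 60% success rate widens from ±10.7 points (1.96 √(0.24/80)) to ±10.9 points (1.96 √(0.24/78)).

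**The case against.** The strongest defence is that a log-rank analysis does not discard a patient who is lost; it censors that patient, who counts up to the time of loss. If the 5% were lost evenly over the year, about half their follow-up would be kept, the allowance would be 2.5%, and 80 × 1.025 = 82 exactly. In simulation, 82 enrolled with 5% censored evenly over the year has power of about 81%, practically the same as 80 complete patients. On that reading nothing is short.

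This could be how 82 arose, but the protocol does not say so, and its wording fits poorly. The 5% is a loss of data that also covers protocol deviations and incomplete data, not censoring alone. The primary endpoint is a success rate at 1 year, for which a patient without 1-year status is not simply half a patient. If half credit was intended, it is an unstated assumption and the text still needs correcting. What stands is that the figures of 78 evaluable and 2.4% tolerated loss assume that the lost 5% contribute nothing.

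It is also fair to say that the effect is slight. Under the one-sample log-rank reading, 79.9% is as good as 80%. Under the proportion test, 80 patients already fall short of 80% power, so the loss allowance is not what causes the shortfall there. Both remarks limit the consequence; neither makes 80, 5% and 82 agree.

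**Conclusion.** The concern holds. Taking the required 80 and the 5% loss as stated, the enrolment target should be 85, not 82. With 82 enrolled and 5% contributing no data, about 78 are evaluable, two fewer than required.

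The arithmetic rests only on the protocol's own numbers and on reading the 5% as patients removed from the analysis. The power cost, about one percentage point, further assumes a comparison with a fixed 74% reference. The base of 80 is taken as given here; whether it follows from the stated rates is a separate question. This is a small error in effect, but an error in a core design figure.

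**What to change.** Make 80, 5% and 82 agree in the synopsis and in sections 7.1, 7.2 and 13. Any one of these would do:

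1. Keep 82 and 5%, state that this leaves 78 evaluable patients, and give the power at 78 with the test and reference used to compute it.
2. Keep 82 and 80, and state that the target tolerates a loss of 2.4%.
3. Keep 80 and 5%, and set the target at 85.

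Options 1 and 2 change wording only; their price is a slightly less favourable stated power or loss allowance. Option 3 costs three more patients and the time to recruit them. If 82 was reached by giving lost patients partial credit for follow-up, the protocol should say so and state the assumed timing of losses.

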7.3 Estimated time needed to enrol this subject population

Subject screening and enrolment will be carried out for approximately 12 months. The study will continue up to 12 months after last patient enrolment, dependent on the rate of enrolment and the regulatory timeline (as applicable).

8. SELECTION OF PATIENTS

8.1 Number of patients planned

All patients referred to the Department of Arrhythmology for the management of paroxysmal or persistent AF will be considered for eligibility. A subject, who meets all of the inclusion criteria, and none of the exclusion criteria, is eligible to participate in this study.

All subjects enrolled in the clinical study (including those withdrawn from the clinical study or lost to follow-up) will be accounted for and documented, assigning an identification code linked to their names, alternative identification or contact information.

This log will be kept up to date throughout the clinical study by the principal investigator (PI) or his/her authorized designee. To ensure subject privacy and confidentiality of data this log must be maintained throughout the clinical study at the clinical site.

8.2 Inclusion criteria

To participate in this clinical subject, the subject must meet all of the following inclusion criteria:

- Age between 18 and 85 years
- Paroxysmal or persistent AF

- Patients AF who have indications for the first time ablation procedure according to the ESC / EHRA recommendations (European Society of Cardiology / European Heart Rhythm Association).
- Ability to provide written informed consent for study participation and be willing and able to comply with the study evaluations and follow up schedule

8.3 Exclusion criteria

Subjects are not eligible for clinical study participation if they meet any of the following exclusion criteria:

- Previous AF ablation procedures
- Secondary AF due to other causes
- Hyperthyroidism
- Left ventricular ejection fraction <30%
- NYHA class IV
- Left atrium area > 35 cm²
- Severe disease of cardiac valves
- Contraindication to anticoagulant therapy
- Presence of thrombus in the left atrium
- Myocardial infarction or unstable angina or recent coronary artery bypass (<6 months)
- Thoracic surgery for congenital, valvular or aortic disease
- History of cerebrovascular events
- Pregnancy
- Significant comorbidity, such as cancer, severe kidney failure requiring dialysis, severe obstructive pulmonary disease, cirrhosis, with a life expectancy of less than 2 years
- Contraindications are present as indicated in the “instructions for use” of the devices used

9. TREATMENTS

9.1 Device used for the ablation procedure

- HeartLight Endoscopic Ablation System (CardioFocus, Inc, Marlborough, MA)

All devices are CE marked and used according to registered indications and according to normal clinical practice.

9.2 Procedures

The clinical study will be conducted in accordance with the CIP. All parties participating in the conduct of the clinical study will be qualified by education, training, or experience to perform their tasks and this training will be documented appropriately.

9.3 Enrollment visit

All patients will undergo screening for the inclusion/exclusion criteria outlined in section 8, to determine the patient’s eligibility for participation in the study. Once it has been determined that the patient meets eligibility criteria, the PI, or designee, is responsible for obtaining informed consent from each prospective study patient prior to commencement of study procedures. Complete an Enrollment Case Report Form (CRF) and record enrolment information in the hospital records in a timely manner (recommended within 5 days).

If a subject does not meet all inclusion criteria or meets any of the exclusion criteria, the subject cannot participate in the study and cannot be enrolled.

In case the subject was already consented to participate in the study, but does not meet inclusion/exclusion criteria, the following actions will be taken.

If study procedure has not occurred:

- Document enrolment information (name of the study, date of consent and inclusion/exclusion) in the hospital records; complete the Enrollment and Withdrawal CRFs. The form must be authorized / approved by the PI or delegated investigator.
 - Inform the subject about the withdrawal.
 - The EC and CA should be notified appropriately about any deviations with regards to obtaining the informed consent.

If study procedure has occurred:

- Document enrolment information (name of the study, date of consent and inclusion/exclusion) in the hospital records; complete the Enrolment and Withdrawal CRFs. The form must be authorized / approved by the PI or delegated investigator.
 - Complete study deviation for inclusion/exclusion not met
 - The EC and CA should be notified appropriately about any deviations with regards to obtaining the informed consent.
 - Subjects will be followed as per physician discretion.

9.4 Baseline Visit

- The following information will be collected at the baseline visit
 - Demographics- include subject's Year of Birth and Gender
 - Physical examination- include subject's height, weight, blood pressure (measurements taken during visit)
 - AF History (first episode, frequency and duration of AF episodes, previous treatment, primary indication for AF ablation)
 - Medical History- indicate subject's risk factors, relevant co-morbidities, previous cardiac procedures
 - Medication (only chronic cardiac related medication)- indicate the drug category the subject is currently taking on a long term base, i.e. no short term medication
 - NYHA classification
- The following activities will be performed at the baseline visit:
 - 12-lead ECG
 - Echocardiogram

Patients will be given a diary for recording AF-related signs/symptoms and instructed to bring it back for follow up visits. A patient number will be assigned, following chronological order.

9.5 Laser balloon ablation Procedure

Selective PV angiography is commonly used prior to positioning of the laser balloon within the target PV ostium. No 'over-the-wire' mechanism is offered, however, an atraumatic soft tip situated at the distal portion of the balloon facilitates safe manoeuvring within the left atrium.

Once in proper position the balloon is filled and continuously flushed with heavy water (deuterium, D2O). Heavy water does not absorb laser energy. The balloon size ~~can~~ be increased in nine

incremental steps from 9 to 35 mm in diameter, depending on the filling pressure within the compliant balloon. Once the balloon is inflated and in proper contact with the opposing tissue, the operator steers the aiming beam to the desired position. A single laser application spans a 30° angle. To ensure a contiguous circular lesion set, adjacent lesions should overlap by 30–50%. Energy delivery can be adjusted from 5.5 W to a maximum of 12 W. Higher energy selection will result in a greater number of acutely isolated PVs following completion of the initial circumferential lesion set. Along the anterior aspect of the septal and lateral PVs power is set to 12 W delivered over 20 s. Along all other locations a maximum power of 10 W for 20 s is used. If perfect sealing between balloon surface and target tissue is not achieved, power should be decreased to 5.5 W delivered over a length of 30 s. Laser ablation may target each PV individually or attempt wide circumferential PVI similar to conventional radiofrequency ablation. However, circumferential isolation should only be attempted if the ipsilateral inferior PV ostium is visualized when targeting the superior PV and vice versa in order to complete the circumferential lesion set at the level of the carina. Since the distance between the right superior and inferior PVs is often greater than between the lateral PVs, circumferential ablation of the septal PVs may only be feasible in a small number of patients. Electrical cardioversion may be performed at the end of the procedure.

Technical information will be recorded in the e-CRF.

- Procedural details
- Duration of ablation
- Sites of ablation
- Substrate characteristics
- Procedural success
- Medications
- AEs and procedure-related complications

10. Assessments and procedures

10.1 *Efficacy*

The primary efficacy endpoint is the freedom from any AF or atrial tachycardia (AT) assessed from the end of the 1 month blanking period to 1 year following the ablation procedure, documented by ILR/ECG Holter monitoring.

Results of the following clinical and instrumental assessments will be recorded.

10.2 *Clinical assessment methods*

- Demographics and medical history: at baseline;
- Cardiovascular history, AF symptoms as referred by the patient: at all visits
- Concomitant medications: at all visits;
- Adverse events: at all visits

10.3 *Instrumental evaluations*

- Routine ECG at baseline, post procedure and/or prior to discharge and then at subsequent visits, as clinically indicated;
- Echocardiogram: at baseline, and at all visits;
- 12-lead ECG: at all visits;
- ILR/ECG Holter monitoring as appropriately assessed by the physician at each follow-up;

